#### 8.2.2. Analysis of secondary outcomes

The proportion of negativization of *T. cruzi* PCR detection either at the end of treatment and/or the end of follow-up at 2 years will be analyzed for all participants using Chi-square test. This analysis will also include only those who were positive PCR test to *T. cruzi* at baseline to compare the proportions of the negativization of *T. cruzi* PCR in each treatment group. Logistic regression model will also be employed to incorporate the potential confounding factors. Frequencies and percentages per arm, an Odds Ratio(OR) measuring the treatment effect and its 95% CI will also be reported. With the repeated measurements of PCR at baseline, after termination of the therapy (i.e., 40-80 days), at 2 years and at the end of follow-up, a longitudinal data analysis technique known as a generalized estimating equation (GEE) will be used to compare the differences in changes of the proportion of negativization of *T. cruzi* over time between BNZ and placebo groups. A within-subject correlation structure for the repeated measurement will be carefully chosen before carrying out a GEE analysis by examining the correlation structure of observed data.

The comparisons for new development of echo changes, new 12 lead ECG alterations, and the progression of NYHA functional class by at least one category will be performed using a chisquare test for categorical variables. The treatment effect will be estimated using a logistic regression including treatment group as a covariate. OR and 95% CI will be reported. Multiple logistic regression will be performed in order to incorporate the potential confounding factors. For continuous variables such as the echo changes, the non-parametric test will be used to compare the treatment effect.

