EVALUATION CRITERIA	
 
-PRIMARY OUTCOME-
 
The first occurrence of any component of the following cluster over the duration of follow-up: 
 
Death
 
Resuscitated cardiac arrest
 
Documented sustained ventricular tachycardia requiring cardioversion
 
Insertion of pacemaker or implantable cardiac defibrillator-
 
Thromboembolic phenomena (stroke, pulmonary or systemic embolism)
 
New development of symptomatic heart failure (HF) characterized by 2 out of 4 of the following: a) signs and symptoms of HF (orthopnea, paroxysmal nocturnal dyspnea, shortness of breath, edema); b) Chest X-Ray: pulmonary congestion; c) need for intra-venous therapy (diuretics, inotropes); d) hospital admission due to HF
 
 
 

	6
EVALUATION CRITERIA	
 
-SECONDARY OUTCOMES-
 
Additional data will be collected in subgroups of patients to investigate other hypotheses:
 
PCR response to treatment
 
New development of any of the following echo changes; segmental wall motion abnormalities, ventricular aneurysm, reduction in LV ejection fraction > 5%, increase in LVDD > 5,0 mm compared with baseline.
 
New 12 lead ECG alterations (complete bundle branch block, fascicular block, advanced atrio-ventricular block, atrial fibrillation, etc).
 
Progression of NYHA functional class by at least one category.
 

VISIT SCHEDULE/STUDY PROCEDURES	
 
Screening & randomization visit
 
Baseline and initiation visit (Day 0)
 
Follow-up visits after 11± 2 days, 3 weeks± 3 days, 40 to 90 days (end of treatment period with a maximum tolerance of 10 days after the last day of drug or placebo administration), 6 months, 12 months and annually from then on, until the end of the study.
 
ECG recordings at baseline, 24 months and study end (all patients)
 
2D-echo at baseline, and final follow-up visit – all patients
 
Blood sample for hematological changes (WBC) and liver and renal function tests (AST, ALT, creatinine) during the treatment period (three-weeks and 2-months visits)
 
Blood sample for central analysis (quantitative serological tests) at baseline and at final follow-up visit – (substudy)
 
Drops of blood sample/ blood sample 5-10ml on filter papers for PCR at baseline, at 24 months, and final follow-up visit (substudy)
 

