#### 4. STUDY DESIGN AND TREATMENTS

#### 4.1 Sample Size Calculation

The sample size calculation for this trial is based on observational data indicating that the five year rate for the time to event of the composite endpoint of death, resuscitated cardiac arrest, development of new heart failure, life threatening non-fatal arrhythmias, thromboembolic phenomena, and need for pacemaker implantation or ICD in the placebo group will be around 30%. Event rate calculations were based on pooled data from longitudinal population studies in patients with  $CD^{35, 36}$ . These studies indicate a 5% annual mortality with sudden cardiac death being responsible for 60% of the mortality. However, event rates among patienta entered into trials is generally lower so we have assumed a 3% -4% annual mortality. It is expected that the annual morbidity rates will also be similar givingh a composite event rate of 6%-8%/yr.

In order to have 90% power at the 5% significance level (two sided) with an overall drop-out rate of 20%, to detect a 20% risk reduction the trial will require the enrolment of at least 3000 patients. Analysis of the primary and secondary outcomes will be performed according to the intention-to-treat principle.

A sensitivity analysis wil be performed in patients with prior sustained ventricular tachycardia, thromboembolic phenomena or heart failure hospitalization. This analysis will allow that the mentioned events are not included as a primary outcome. Also, in patients with advanced AV block at onset, pacemaker insertion will not be counted as an endpoint.

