#### 4.2.3 Method of assigning patients to treatment group

The patient identification (ID) and treatment numbers will be provided at randomization by a centralized randomization service located at the Brazilian Coordinating Center. A system similar to that used in the CREATE and HOPE trials conducted by the PHRI will be designed. Alterbatively if all sites have access to a computer with internet access, local randomization may be performed in a secure way. Randomization will be 1:1 with stratification according to centre using a random block size. Subsequent treatment numbers for study drug re-supply will be provided.

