## 7.2 Missing data

Missing data will be vigorously pursued with the quality assurance process. Centres will be requested to collect as much information as possible. In general missing values will be treated as missing, unless otherwise specified. Unknown data will be coded as such in the database and classified as such on any analysis. No attempt will be made to impute missing values and only observed values will be used in the analyses. Depending on the assessment, analyses may not include all patients in an analysis population, because certain patients in the intended population may have missing data.

Patient mortality and morbidity will be determined for all participants regardless of compliance with study medication or visit schedule. For patients who die prior to follow-up evaluation of LV function or ECG, and worse case rank will be assigned to that patient and a secondary non-parametric analysis will be done to examine the sensitivity to these missing data.

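### The continuous echo measures are tested without the baseline value as a covariate, and the analysis that accounts for deaths should stand beside the observed-only echo result

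*Supplement*

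**What the plan says.** SAP 8.2.2 deals with the echo, ECG and NYHA outcomes in two ways.

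- **Binary outcomes** (new echo abnormality, new ECG abnormality, NYHA worsening): a chi-square test, a logistic model with treatment alone, and then a multiple logistic regression for potential confounders that are not listed.
- **Continuous echo measures**: "For continuous variables such as the echo changes, the non-parametric test will be used to compare the treatment effect". Neither the test nor any covariate is named.

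SAP 8.1.2 defines the LVEF and LV diameter outcomes as changes relative to baseline.

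SAP 7.2 sets the general rule: "No attempt will be made to impute missing values and only observed values will be used in the analyses". It then adds a provision for deaths: "For patients who die prior to follow-up evaluation of LV function or ECG, and worse case rank will be assigned to that patient". That provision is described as a secondary non-parametric analysis of sensitivity to missing data. It mentions LV function and ECG but not NYHA class.

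The latest protocol's Clinical Trial Summary schedules "2D-echo at baseline, and final follow-up visit" for all patients, and ECG at baseline, 24 months and study end. SAP 8.1.1 says in general terms that efficacy parameters are recorded at month 6, yearly and at the final visit. It does not name echo or NYHA there.

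**The concern.** Whether benznidazole halts or reverses loss of LV function is a stated secondary objective of the protocol, and LVEF and LVEDD are its direct measures. Each patient should have a baseline value, and the later value is normally correlated with it. Subtracting baseline uses part of that information; fitting baseline as a covariate uses it more efficiently. A standard two-sample rank test, such as the Wilcoxon test that SAP section 5 uses for baseline tables, takes no covariates. As written, therefore, the continuous echo comparison forgoes precision that costs nothing in data or patients.

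The second issue is who contributes to that comparison. With one follow-up echo, years after randomisation, a patient who dies has no value and leaves the main comparison. If treatment affects death, the surviving groups need not be comparable. The SAP's own remedy, the worst rank, has only secondary status, is not tied to a baseline-adjusted method and does not cover NYHA.

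**Working it through.** **The plan's own figures.** The documents state no power or sample size for the echo, ECG or NYHA outcomes. Protocol 4.1 sizes only the primary composite. With 30% against 24%, two-sided 5% and 90% power, a continuity-corrected comparison of proportions gives 2,364 patients. Dividing by 0.80 for 20% drop-out gives 2,955, in line with the stated minimum of 3,000. That calculation does not bear on the precision of LVEF or LVEDD.

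**Step 1: gain from baseline adjustment.** Let baseline and follow-up have equal variance s² and correlation rho.

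- Change score: variance 2s²(1 − rho)
- ANCOVA on baseline: variance s²(1 − rho²)
- Ratio: (1 − rho²) / [2(1 − rho)] = (1 + rho)/2

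The documents give no rho, so a range is assumed:

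| rho | variance ratio | extra patients needed without adjustment |
|---|---|---|
| 0.5 | 0.75 | 1/0.75 − 1 = 33% |
| 0.7 | 0.85 | 1/0.85 − 1 = 18% |
| 0.8 | 0.90 | 1/0.90 − 1 = 11% |

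The formula is for means. For a rank test against rank ANCOVA it is only a guide.

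**Step 2: deaths before the follow-up recording.** Inputs are annual mortality of 3-4% (protocol 4.1), mean follow-up of 5.5 years (SAP 7.1) and 2,855 patients (SAP section 2). Share dead by time T = 1 − exp(−mT).

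- Echo (T = 5.5): 1 − exp(−0.165) = 15.2%, and 1 − exp(−0.22) = 19.7%. That is about 434 to 564 patients.
- ECG (T = 2, first scheduled follow-up recording): 1 − exp(−0.06) = 5.8%, and 1 − exp(−0.08) = 7.7%. That is about 166 to 220 patients. Later deaths still miss the study-end ECG.
- NYHA: if class is among the parameters recorded at month 6 and yearly, the share with no follow-up value is smaller still. The SAP does not say so outright.

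These counts apply the assumed mortality to both arms.

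**Step 3: what leaving out deaths can do.** The following figures are all assumed, for illustration. Mortality is 18% on placebo and 14.4% on drug. Echo worsening is 40% among those who would survive on either arm and 80% among the 3.6% saved by the drug.

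- Observed only, drug: (0.82 × 0.40 + 0.036 × 0.80) / 0.856 = 41.7%, against 40% on placebo. The odds ratio is about 1.07, against a drug that saves lives.
- Death counted as worsening: 14.4% + 35.7% = 50.1% on drug, against 18% + 32.8% = 50.8% on placebo.

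The shift is small but can change direction, which is why both results should be visible.

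**The case against.** Several points can fairly be made for the plan, and most of them stand.

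- A reader might infer that all the echo, ECG and NYHA outcomes are analysed without adjustment. They are not: the binary outcomes also get a multiple logistic regression. Its weakness is that the covariates are unnamed, and it does not reach the continuous measures.
- A reader might infer that the baseline echo is discarded. It is not, because the outcomes are defined as change from baseline or as new findings. The loss is of efficiency and introduces no bias.
- A reader might apply 15-20% to all three outcomes. It fits echo only.
- The number of deaths is not the size of any bias. Distortion comes mainly from a difference in deaths between arms. If the planned composite reductions (20% in the protocol, 26.5% in the SAP) applied to death, that difference would be about 0.152 × 0.20 = 3 to 0.197 × 0.265 = 5 percentage points. With no effect on death, no systematic difference in numbers is expected.
- Death is already a component of the primary outcome, and SAP 7.2 already plans a worst-rank analysis. Making death count as worsening in the main binary analyses would let those outcomes partly reflect mortality and overlap with the primary composite. Statisticians may reasonably differ on this.

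The objection does not answer two things: the continuous echo test has no covariate, and the death rule is silent on NYHA and on the method to be used with baseline.

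**Conclusion.** The point holds in limited form. The plan gives the continuous LVEF and LVEDD comparisons an unnamed test with no baseline covariate, and nothing else in SAP 8.2.2 supplies one. The cost is a variance about 11% to 33% larger than necessary, assuming rho between 0.5 and 0.8 and equal variances at the two times; neither assumption comes from the documents. On the protocol's mortality assumption, about 15-20% of patients would be missing from the main echo comparison through death, so the worst-rank result is needed to read it. For ECG the corresponding figure is about 6-8% before the first follow-up recording, and for NYHA probably less.

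The documents do not support calling the observed-only binary analyses an error, nor saying that the SAP ignores deaths. The primary outcome is unaffected.

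**What to change.** In SAP 8.2.2, replace the unnamed test for the continuous echo measures by ANCOVA, or rank ANCOVA, of LVEF and of LVEDD with the baseline value of the same measure as covariate. Name the covariates of the multiple logistic regression.

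In SAP 7.2, state that the worst-rank analysis of deaths is reported beside the observed-only echo result and uses the same baseline-adjusted rank method. Extend the rule to NYHA. State for each binary outcome whether death before assessment counts as worsening in the main analysis; either choice is defensible if declared.

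No new data or patients are needed. SAP section 2 allows changes by people blinded to outcomes by treatment group until sign-off before database lock. The cost is slightly more analysis work and one more result to report per measure.

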## 9. SAFETY

## 9.1. Safety Variables

Adverse events (AEs) during the active therapy phase recorded during follow-up visits at 11 and 21 days and at the end of therapy (40 to 80 days) will be closely monitored and reported.

A serious adverse event (SAE) is defined as any untoward medical occurrence that is observed at any dose:

- Results in death or
- Is life threatening or
- Requires in-patient hospitalization, or prolongation of existing hospitalization or
- Results in persistent or significant disability/incapacity or
- Is a medically important event

All adverse events in each treatment group regardless of seriousness or relationship to study drug are to be reported. Whenever possible, symptoms should be grouped as single syndrome or diagnosis.

## 9.2. Safety Analysis

All randomized patients to BNZ/Placebo will be included in the analysis. The AEs and SAEs will be counted on the date of first dose administered and up to 30 days after administration of the last dose of treatment assigned. Safety will be summarized by tabulations of AEs and SAEs for each treatment group. The analysis of safety will be mainly descriptive. For all safety analyses, the day of the first dose of study medication will be assumed to have occurred on the same day as randomization unless there is a record indicating that study medication was not used immediately after randomization. The separate summaries of adverse events and serious adverse events will be provided by the period of observation, i.e., whether the (serious) adverse event was observed while a patient was on the study medication or after the termination of the study drug use.

All adverse events will be classified on the basis of Medical Dictionary for Regulatory Activities (MedDRA) terminology and summarized for each treatment. Each adverse event will be recorded with a system organ class and a preferred term. In reporting incidence, each subject will be counted only once within a system organ class or a preferred term, and counts will be provided for each treatment group. Percentages will be calculated using the number of randomized patients in each treatment group. For events of particular interest, summary statistics (n, mean, standard deviation, median and range) may be calculated with the time from randomization to onset and the duration

of events. The list of adverse events and serious adverse events will be provided by patient with details of the events.

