#### 1.8.3. Benznidazole; Mechanism of Action, Efficacy and Safety in patients with CD

Benznidazole (N-benzil-2nitro-1imidazole-acetamide) has direct action against both the trypomastigotes and intracellular amastygotes, probably by affecting reductive stress, which involves covalent modification of macromolecules by nitroreduction intermediates. The recent demonstration that  $T \ cruzi$  strains which over-express superoxide dismutase have increased sensitivity to benznidazole lends support to this mechanism. The activity of these compounds may be enhanced by selectively interfering with the parasite's redox state. This possibility is also supported by the recent discovery of trypanothione and trypanothione reductase, a unique system which replace glutathione and glutathione reductase in trypanosomatids as the main intracellular thiol-redox system^83. Although there is an active search for specific trypanothione reductase inhibitors have shown significant anti-parasitic activity, either *in vitro* or *in vivo*. Thus, benznidazole remains as the only adequate compound to test in appropriately designed clinical trials.

The efficacy of benznidazole in the chronic stages of CD can only be determined by testing the hypothesis that trypanocidal treatment can impact the evolution of disease, preventing or delaying the development of defined clinical forms, no matter what happens with the results of the serological and parasitological tests in the treated and untreated patients. An investigation designed for this purpose should also clarify the unclear safety profile of treatment with benznidazole.

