#### 4.2.2 Randomization

Patients recruited following strict inclusion and exclusion criteria will be randomized double-blindly to receive 300mg/day of benznidazole in two daily doses for 40 to 80 days or matching placebo using the same administration daily scheme.

As seen on the Table for the Therapeutic Dosage, in page 5, both groups will be treated for 40 to 80 days, according to a direct relationship with the patient's weight: thus, a patient weighing 40kg will be treated with 300mg daily for 41 days, weighing 51kg, for 51 days, 65kg = 65 days and so on, up to the maximum of 80kg, when a patient with this last weight will receive 300mg daily for 80 days. Hence, the maximum dose to be received, even for patients weighing more than 80 kg will be, at the end o the treatment period, 24g

Patients will be followed with attention paid to development of side effects including dermatitis, leucopenia, peripheral neuropathy and gastrointestinal symptoms. Potential toxic effects will be scrutinized with clinical and laboratory evaluation, including white cell count and hepatic function tests (AST, ALT, serum creatinine). These evaluations will be conducted at baseline, three weeks and 40 to 90 days after the beginning of treatment.

- Additional data will be collected in subgroups of patients to investigate other hypotheses:

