#### 4.2.5 Treatment adherence

Study continuation is recommended unless clear contraindications arise, study drug should be continued or only briefly interrupted ( $\leq$  less than 1 week). The only clear criteria for permanent discontinuation of benznidazole study medication are: (i) significant leukopenia (< 2,500), (ii) serious gastrointestinal symptoms (iii) severe allergic dermopathy, and (iv) peripheral sensitive neuropathy. In other situations, discontinuation of study drug will be discouraged as much as possible. Symptomatic treatment for mild symptoms (nauseas, vomiting, allergy) is allowed. Study drug accountability, as well as all pre-specified concomitant medications, must be appropriately recorded at each scheduled visit.

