## 3.2 Secondary objectives

The secondary objectives are the following:

- To determine the effects of BNZ compared to placebo regarding negativization of PCR in patients with chronic CCC after 60-80 days of treatment and at 24 months and end of follow-up.
- To evaluate whether BNZ prevents new development of any of the following echo changes; segmental wall motion abnormalities, ventricular aneurysm, reduction in LV ejection fraction > 5%, increase in LVEDD > 5.0 mm compared with baseline.
- To evaluate whether BNZ prevents new 12 lead ECG alterations (complete bundle branch block, fascicular block, advanced atrio-ventricular block, atrial fibrillation(AF), etc).
- To evaluate whether BNZ prevents the progression of NYHA functional class by at least one category.
- To evaluate the safety, tolerability and adherence to BNZ in patients with CCC.

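### SAP 9.2 does not define the four toxicities named in the protocol as grouped events and plans no between-arm difference with a confidence interval for any harm

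*Supplement*

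**What the plan says.** SAP 3.2 lists among the secondary objectives: "To evaluate the safety, tolerability and adherence to BNZ in patients with CCC". Protocol 1.8.3 gives the reason: "An investigation designed for this purpose should also clarify the unclear safety profile of treatment with benznidazole".

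The toxicities of interest were known in advance. Protocol 4.2.2 (the February 2009 version, to which the SAP refers) says: "Patients will be followed with attention paid to development of side effects including dermatitis, leucopenia, peripheral neuropathy and gastrointestinal symptoms". Protocol 4.2.5 builds its criteria for permanent discontinuation on the same four, and protocol 7.3 singles out severe dermatitis and neuropathy for monitoring by the DSMB. White cell counts are scheduled at baseline, at three weeks and at the end of treatment.

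On analysis, SAP 9.2 says: "Safety will be summarized by tabulations of AEs and SAEs for each treatment group", and "The analysis of safety will be mainly descriptive". Events are coded in MedDRA, and "each subject will be counted only once within a system organ class or a preferred term". Percentages use the randomised patients of each arm as denominator. Separate summaries for on-drug and off-drug periods and by-patient listings are also planned. Events of particular interest may get onset and duration summaries, but the SAP does not say which events these are. SAP 6 adds the frequency of drug interruption and the reasons, by arm. SAP 9.1 asks that symptoms be recorded as one syndrome or diagnosis where possible.

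**The concern.** A safety objective for a drug with four known toxicities raises two questions for each: how many patients in each arm had it, and how much of that is attributable to the drug. The SAP commits to neither answer at the level of the named toxicity.

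The first depends on definition. If skin reactions are coded under more than one preferred term, no single term row gives the incidence of dermatitis, and the organ-class row also takes in other skin events. The same can happen with neuropathy among nervous-system events, and with leucopenia.

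The second depends on the effect measure. A benefit-risk statement would set a hazard ratio and interval for the primary outcome against two bare percentages for each harm. If groupings and contrasts are chosen only after unblinding, they lose the protection of pre-specification, which SAP 2 gives as the purpose of the plan.

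**Working it through.** The documents state no safety effect, safety power or safety precision, so there is no figure of the plan's own to reproduce. The check compares the sections and then computes what precision is available.

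**1. Treatment contrasts in the SAP**

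| Objective | Section | Planned contrast |
|---|---|---|
| Primary composite | 8.2.1 | HR with 95% CI, logrank test |
| PCR negativization | 8.2.2 | OR with 95% CI, chi-square test, GEE |
| New echo changes, new ECG alterations, NYHA progression | 8.2.2 | OR with 95% CI, chi-square test |
| Adverse events | 9.2 | n and % per arm; no difference, ratio or interval |
| Drug interruption and reasons | 6 | Summary per arm; no difference, ratio or interval |

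SAP 10 (subgroups) and 11 (sensitivity) add nothing on safety. Section 9 plans no analysis of the white cell counts taken on treatment.

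**2. What the planned rows yield for each named toxicity**

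- Gastrointestinal symptoms: this is itself a body-system category. The organ-class row counts each patient once, so it comes close to what is needed.
- Dermatitis, leucopenia, neuropathy: no grouping is defined. If a toxicity falls under k preferred terms with r₁ … r_k patients, the number of patients with the toxicity lies between max(rᵢ) and Σrᵢ. The term counts alone do not say where, because one patient can appear in several rows. As a hypothetical case, three rows of 4% each allow a true incidence anywhere from 4% (all the same patients) to 3 × 4% = 12% (no overlap). The documents do not show how events would be coded, so the number of rows is an assumption.

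**3. Precision available for a risk difference**

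Inputs: 2,855 randomised (SAP 2; 1,543 + 1,312 = 2,855), allocation 1:1 (protocol 4.2.3), so n = 2,855 / 2 ≈ 1,427 per arm.

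95% half-width = 1.96 × √[p₁(1−p₁)/n + p₂(1−p₂)/n]

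- 12% v 8% (assumed): 1.96 × √[(0.1056 + 0.0736)/1,427] = 0.0220, or ±2.2 points around +4.0.
- 2% v 1% (assumed): 1.96 × √[(0.0196 + 0.0099)/1,427] = 0.0089, or ±0.9 points around +1.0, giving 0.1 to 1.9.
- 11.5% v 8.3% (illustration only): half-width 2.2 points around +3.2, giving 1.0 to 5.4.

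The last pair is the withdrawal for side effects in the small adult randomised trial cited in protocol 1.8.2, with arms of 26 and 24. The percentages correspond to 3/26 and 2/24. They cover any side effect over 30 days of treatment and are not the incidence of one named toxicity. They serve only to place the order of magnitude.

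**The case against.** The strongest reply is that descriptive safety tables are normal practice, that no protocol section promises a safety effect measure or test, and that the missing interval biases nothing, since coding is the same in both arms and the primary analysis is untouched. That stands: the present plan is not an error.

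A reader might also infer three stronger things that the documents do not support.

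- That safety is only tabulated by class and term. Period summaries, listings, optional onset and duration summaries, and interruption reasons by arm are planned too. The interruption table may show much of what led to stopping the drug.
- That the safety objective has no estimate at all. Percentages per arm on a fixed denominator are planned. For any row that exists, a reader can work out a difference and interval from the two percentages and arm sizes. What is missing is a planned between-arm estimate with its uncertainty, and a row for each toxicity.
- That the four toxicities are certainly split and therefore understated. The instruction in SAP 9.1 to record a syndrome or diagnosis works against splitting, and gastrointestinal symptoms are largely served by the organ-class row. But that instruction concerns how symptoms are reported; it does not pool different diagnoses across patients. Two patients whose skin reactions are recorded under different diagnoses would still sit in different term rows.

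So splitting is possible and its extent unknown. The reply that readers can do the arithmetic themselves fails where the patients cannot be de-duplicated from the published rows.

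**Conclusion.** The point holds as a free improvement. The SAP plans per-arm incidence by coded term and class but leaves the four toxicities that the protocol itself names without a grouped definition, and it plans no drug-attributable estimate with an interval for any harm. The effect is on the completeness of the answer to a listed secondary objective, not on the validity of any planned result.

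The trial is large enough to give a useful answer: half-widths of roughly 0.9 to 2.2 points over the assumed range from 2% v 1% to 12% v 8%. This rests on equal arms of about 1,427, all randomised patients as denominator, and rates that the documents do not give for any named toxicity. How far dermatitis, leucopenia or neuropathy would be scattered over rows cannot be known from the documents.

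**What to change.** In SAP 9.2, before unblinding:

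1. Name the four toxicities of protocol 4.2.2 as the events of particular interest.
2. Fix a preferred-term list for each. For leucopenia, also use the scheduled white cell counts, with the laboratory definition written down in advance.
3. Count each patient once per toxicity.
4. Report n and % by arm, and the risk difference with its 95% CI, without a formal test, both overall and for events leading to permanent discontinuation.
5. Keep the existing class and term tables, period summaries and listings.

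The cost is a term list drawn up by staff who are blinded to treatment and a few further rows of output, from data already scheduled for collection. SAP 2 already allows blinded revisions until sign-off before database lock. There is no material downside; without a test, no multiplicity question arises.

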## 4. POPULATIONS TO BE ANALYZED

### 4.1 Intention-to-treat Population

All patients who are randomized are included in the analysis according to the treatment groups to which they were randomized, irrespective of whether or not the patient actually received study drug, the patient's compliance with the study protocol or duration of the trial participation. All analyses of primary and secondary endpoints, as well as baseline summaries, subgroup analyses and all analyses related to safety will be based on the intention-to-treat(ITT) principle. Sensitivity analyses for the primary and secondary outcomes will be performed based on the following two sub population A and B.

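### Adverse-event percentages divide by all randomized patients although events count only from the first dose; a dosed denominator and a recorded first-dose date would be a cheap improvement

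*Supplement*

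**What the plan says.** SAP 4.1 places safety on the same footing as efficacy: "all analyses related to safety will be based on the intention-to-treat(ITT) principle", and the ITT population holds every randomized patient "irrespective of whether or not the patient actually received study drug".

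SAP 9.2 repeats this ("All randomized patients to BNZ/Placebo will be included in the analysis") and sets the denominator: "Percentages will be calculated using the number of randomized patients in each treatment group". The same section ties the numerator to dosing: "The AEs and SAEs will be counted on the date of first dose administered and up to 30 days after administration of the last dose".

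For the time origin, SAP 9.2 says that "the day of the first dose of study medication will be assumed to have occurred on the same day as randomization", with the exception "unless there is a record indicating that study medication was not used immediately after randomization". For events of particular interest, it allows, but does not require, summaries of the time from randomization to onset.

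The latest protocol's Clinical Trial Summary lists a screening and randomization visit and, as a separate item, an initiation visit on Day 0. Protocol 6.1 times the 11-day and 3-week safety visits from the start of treatment. Protocol 4.2.2 does the same for the on-treatment laboratory checks.

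**The concern.** The numerator depends on dosing and the denominator does not. A patient known never to have started has no event window and so cannot be counted as having an event, but still enlarges the denominator. Any such patients can only lower the reported percentages. For safety, that is the non-conservative direction.

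This matters because safety is a stated objective in both documents, and protocol 1.8.3 says that the trial should clarify a safety profile that is not well established. Absolute adverse-event rates are part of that answer.

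The time origin is a second, smaller matter. Where treatment starts after randomization and no record shows it, the default date lengthens the apparent time to onset. It can also move events between the on-drug and after-drug summaries that SAP 9.2 plans. The protocol's own safety schedule runs on a different clock.

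**Working it through.** **1. Is a dosed population defined elsewhere?** On-Treatment Populations A and B (SAP 4.2 and 4.3) are defined by randomization period and regimen, not by drug taken. SAP 4.1 assigns them to sensitivity analyses of the primary and secondary outcomes only. SAP 6 bands compliance, with under 50% as the lowest band, and summarizes interruptions by arm, but does not ask for the number who took no dose. The mismatch in SAP 9.2 is therefore not repaired elsewhere.

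**2. Denominator base.** SAP 2 gives 1,543 + 1,312 = 2,855 randomized, which matches its stated total. With 1:1 allocation this is 2,855 / 2 = 1,427.5 per arm.

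**3. Dilution.** Let d be the share of an arm documented as never dosed. Those patients add no events, so

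reported rate = rate among dosed × (1 − d).

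The documents give no d, so the range below is an assumption. They also plan no adverse-event rate. As illustrations I use figures that protocol 1.8.2 quotes from earlier studies: 12% stopping for side effects in a non-randomized study, and 11.5% (benznidazole) against 8.3% (placebo) withdrawing for side effects in a small randomized comparison.

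| d, both arms (assumed) | Never dosed per arm | 12% reads as | 3.20-point difference reads as |
|---|---|---|---|
| 1% | 14 | 12 × 0.99 = 11.88% | 3.17 |
| 2% | 29 | 12 × 0.98 = 11.76% | 3.14 |
| 5% | 71 | 12 × 0.95 = 11.40% | 3.04 |
| 10% | 143 | 12 × 0.90 = 10.80% | 2.88 |

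**4. Risk ratio.** With equal d, the factor cancels: 11.5 / 8.3 = 1.386 with either denominator. With unequal d it does not:

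- 5% benznidazole, 1% placebo: (11.5 × 0.95) / (8.3 × 0.99) = 1.33
- 1% benznidazole, 5% placebo: (11.5 × 0.99) / (8.3 × 0.95) = 1.44

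**5. Power.** For 11.5% against 8.3%, the two denominators give almost the same power: 80.8% (all randomized) and 80.9% (dosed only) at d = 2%; 79.5% and 79.7% at d = 5%.

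**6. Time origin.** Two groups must be kept apart.

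- *A record shows that drug was not used immediately.* The exception in SAP 9.2 applies and no first-dose date is assumed. If the patient never started, there is no window, and the dilution in step 3 follows.
- *No such record.* The first dose is placed on the randomization day. If the patient in fact never started, events can be counted from that day, so the formula in step 3 does not apply. The end of the window, last dose plus 30 days, is then undefined.

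The documents give no interval between randomization and Day 0, so the shift in onset times cannot be sized.

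**The case against.** The strongest reply is that the all-randomized set is a declared choice. SAP 4.1 makes it in plain terms, and in a double-blind placebo trial it preserves the randomized comparison. That stands as a reason to keep the all-randomized table. It does not remove the mismatch, because an event window that depends on dosing is not a consistent ITT analysis.

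The second reply is that little turns on it. SAP 9.2 calls the safety analysis mainly descriptive, protocol 7.3 sets no formal safety boundaries, and the loss on a 12% rate is under 0.25 points when d is 2% or less. This stands, and it sets the weight of the point.

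The third is that SAP 9.2 already provides counts by arm and patient listings, so a reader could divide again. That works only if the number dosed is reported, and the SAP does not ask for it. It is also true that the onset summaries are optional, and that the protocol's detection visits do not depend on the randomization date.

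A reader might infer more than the documents support:

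- That every never-dosed patient is assigned an assumed exposure. The exception for a record of non-immediate use rules this out for documented non-starters.
- That toxicity will in fact be understated. No passage says that anyone went undosed; two separate visits show only that it is possible.
- That the relative comparison between arms is biased. It is not, if non-start is equal by arm.
- That patients should be regrouped by treatment received. Nothing in the documents points to crossover or misallocated drug.

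**Conclusion.** The point holds as a small, conditional defect. SAP 9.2 pairs a dosing-dependent event count with an all-randomized denominator, and no set of patients with at least one dose exists. Documented non-starters, if there are any, scale each arm's adverse-event rates by (1 − d), and the risk difference too if d is equal in the two arms. The risk ratio changes only if non-start differs by arm. The conclusion on size rests on an assumed d, on illustrative rates taken from earlier studies, and on non-starters being recorded as such.

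The default first-dose date is a separate inconsistency with the protocol's treatment-start clock. It reaches only patients with no record of a delayed start, and its size cannot be estimated from the documents.

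This is a worthwhile low-cost improvement, not a threat to the trial's conclusions.

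**What to change.** In SAP 9.2:

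- Use as the main denominator all randomized patients who took at least one dose, grouped as randomized.
- Time onset from the recorded first dose.
- State how the event window is opened and closed when no dose is recorded.
- Report the number never dosed by arm.
- Keep the all-randomized table as supportive, and adjust the sentence in SAP 4.1 that puts all safety analyses on ITT.

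The cost is a few sentences, one population flag and one extra set of tables. The downside is that the main safety table is no longer strictly ITT; the supportive table covers that.
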